## 1. BACKGROUND

Cataracts are the most common cause of low vision and blindness in the world (Brian and Taylor, 2001). Cataracts occur when the crystalline lens becomes cloudy preventing light from reaching the retina and so resulting in poor vision. Cataract is highly treatable and the surgery involves removing the cloudy crystalline lens and replacing it with a clear artificial plastic lens (made of acrylic) called an Intraocular lens (IOLs) (Foster, 2001).

Around one fifth of people attending for cataract surgery have astigmatism (Swampillai *et al.*, 2020). Astigmatism refers to the imperfection in the curvature of the cornea, the clear and dome-shaped covering in front of the eye. An eye with severe astigmatism is oval (like a rugby ball) instead of round like a football. This oval shape reduces vision and make vision blurry all over, not just close-up, or far away. While most astigmatism orientated with the steep curve vertically, for some, it can be horizontal (the rugby ball on its side) or more rarely, obliquely positioned (neither horizontal nor vertical). Degree of astigmatism is measured in dioptre (D). A perfect eye has zero dioptre. Most people can have between 0.5-0.75 D and people with 1.5D or more typically need to wear contact lenses or eyeglasses for clear vision.

Conventional non-Toric monofocal IOLs is the most common implants used in cataract replacement surgery. They stay focused at one fixed distance and when chosen to correct distance vision error such as short-sightedness, reading glasses may be needed to see thing close-up. Also, these lenses do not correct astigmatism. In most NHS hospitals such as in UHP, astigmatism often is left untreated during the cataract replacement surgery.

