### 10.3.3 Secondary outcome analysis

Outcomes	Data collected	Data type	Quantitative statistical Analysis
Eye glazing characteristics during obstacle crossing and stair walking	Gazing duration on obstacles and area of interest on environment during stair walking  Area of interest determined by heat map (area with highest frequency of gazing)	Interval  Gaze pattern of location of hotspots and duration of gaze will be collected using Tobii pro eye tracker.  % time spent on fixation of highlighted object or area of interest  Best performance among 3 trials will be used.	Mixed ANOVA and post-hoc Bonferroni tests will be used to determine the differences between the Toric IOLs group and Monofocal IOLs group before surgery and 6 months after second eye surgery.
Refraction and visual acuity	-Visual acuity (vision, sphere, Cylinder, Axis, DVA, Add NVA) -IOL tilt and decentration -IOL rotation (for Toric IOL group only)	Interval  Average tilt, decentration and rotation of lens will be analysed by calculating average value in Toric and monofocal groups. Bland Altman will be used to study the agreement of position-level of error for IOLs tilt, decentration and rotation.	Mixed ANOVA and post-hoc Bonferroni tests will be used to determine the differences between the Toric IOLs group and Monofocal IOLs group before surgery and 6 months after second eye surgery.  Unaided and aided distance visual acuity will be recorded in Log MAR and comparisons between the two lenses pre and post cataract surgery will be conducted using a two-way ANOVA. Post-operative refractive astigmatism will be analysed using the Alpins method*. Correlation between SIA and TIA will be assessed, and dependent t-tests will be used to analyse the remaining metrics in the two groups
Questionnaire	Short Fall Efficacy Scale International	Ordinal (non-parametric)	Mixed ANOVA and post-hoc Bonferroni tests will be used to determine the differences between the Toric IOLs group

Vision and balance changes after bilateral implantation of Toric IOLs  
IRAS ID: 286913

	Fear of Falling Questionnaire CAT-PROM 5 Quality of life Questionnaire		and Monofocal IOLs group before surgery and 6 months after second eye surgery.
--	---	--	--

\*Post-operative refractive astigmatism will be analysed using the Alpíns method. Cylindrical power and axis will be converted to vectors (J0 and J45; Equations 1 & 2).

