Equation 1: Calculation of J0	$J0 = J \cos 2\alpha$ 
J0 = cylindrical effect at 180° J = cylindrical power a = axis in radians

Equation 2: Calculation of J45	$J45 = J \sin 2\alpha$ 
J45 = cylindrical effect at 45° J = cylindrical power a = axis in radians

Target induced astigmatism (TIA) is the astigmatic correction predicted to occur and will be calculated with Equation 3.

Surgically induced astigmatism (SIA) is the astigmatic correction achieved post-operatively and calculated as Equation 4.

Equation 3: Target induced astigmatism	$TIA = \sqrt{((PreOp J0 - Predicted residual J0)^2 + (PreOp J45 - Predicted residual J45)^2)}$
Equation 4: Surgically induced astigmatism	$SIA = \sqrt{((PreOp J0 - PostOp J0)^2 + (PreOp J45 - PostOp J45)^2)}$

The Correction index (CI) is the ratio of SIA to TIA (Equation 5) and difference vector is the difference between TIA and SIA (Equation 6).

Equation 5: Correction Index	$CI = SIA/TIA$
Equation 6: Difference Vector	$Difference Vector = TIA - SIA$

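### In the non-Toric arm the correction index and the TIA minus SIA difference score agreement with a prediction of almost no correction, so neither can show the Toric lens's effect on astigmatism

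*Combined protocol and SAP*

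**What the plan says.** Section 10.3.3 analyses post-operative refractive astigmatism by the Alpins method, after converting cylinder and axis to J0 and J45.

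- Equation 3: TIA is the length of the pre-operative vector minus the predicted residual vector. "Target induced astigmatism (TIA) is the astigmatic correction predicted to occur" is the definition given. The predicted residual is not defined separately by arm, and no common target is set.
- Equation 4: SIA is the length of the pre-operative vector minus the post-operative vector. "Surgically induced astigmatism (SIA) is the astigmatic correction achieved post-operatively and calculated as Equation 4" is the wording.
- Equation 5: correction index = SIA / TIA.
- Equation 6: difference vector = TIA − SIA, a subtraction of two lengths.

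The vision row of the 10.3.3 table then says: "Correlation between SIA and TIA will be assessed, and dependent t-tests will be used to analyse the remaining metrics in the two groups".

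Two other places fix what the prediction is for a control eye. Section 1 says of standard monofocal lenses that "these lenses do not correct astigmatism". Section 6.2 excludes patients whose predicted bilateral post-operative corneal astigmatism is below 1.50 D.

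The same table row lists cylinder among the data collected, assigns a mixed ANOVA between the lens groups, and plans a two-way ANOVA of unaided and aided logMAR acuity.

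**The concern.** A correction index of 1 is normally read as full correction, and a difference of zero as hitting the target. Here the target belongs to the eye and the lens it received. For a Toric eye the target is to remove most of the astigmatism. For a non-Toric eye it is to leave nearly all of it in place. Both can be met perfectly, and both then score 1 and 0.

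Section 3.1 makes correction of astigmatism the route by which the Toric lens is expected to improve dynamic stability, and Section 2 wants the results to inform selection of patients for Toric lenses. A published control-arm index at or above 1 would read as full or over-correction in patients whose astigmatism was left alone.

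**Working it through.** **Inputs from the documents.** Equations 3 to 6; no astigmatic correction by the standard lens (Section 1); the 1.50 D exclusion (Section 6.2). The plan states no value for TIA, SIA, the index or the difference, so there is no figure of its own to reproduce. It also gives no mean astigmatism, incision effect or prediction error. Those below are assumptions.

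**Step 1. Worked eyes.** Assumed: pre-operative 2.75 D, incision effect 0.25 D, axis unchanged unless stated.

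| Eye | Predicted (D) | Achieved (D) | TIA | SIA | SIA/TIA | TIA − SIA | Left (D) |
|---|---|---|---|---|---|---|---|
| Non-Toric | 2.50 | 2.50 | 0.25 | 0.25 | 1.00 | 0.00 | 2.50 |
| Non-Toric | 2.50 | 2.40 | 0.25 | 0.35 | 1.40 | −0.10 | 2.40 |
| Non-Toric, axis 4° off | 2.50 | 2.50 | 0.25 | 0.443 | 1.77 | −0.19 | 2.50 |
| Toric | 0 | 0.40 | 2.75 | 2.35 | 0.855 | 0.40 | 0.40 |

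In the third row, 4° of axis is 8° in J0/J45 space, so SIA = √(2.75² + 2.50² − 2 × 2.75 × 2.50 × cos 8°) = 0.443. The corrected eye scores worse than the first non-Toric eye on both metrics.

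**Step 2. Range.** When the prediction is met, the index is exactly 1 and the amount left is the pre-operative value minus the incision effect. Over assumed values of 1.75 to 3.50 D and 0.10 to 0.50 D, that is 1.75 − 0.50 = 1.25 D up to 3.50 − 0.10 = 3.40 D. Applied to each eye, the Section 6.2 exclusion removes the part below 1.50 D. If the predicted incision effect is 0, TIA = 0 and the index is undefined. If one incision effect is used for every control eye, TIA is constant and its correlation with SIA is undefined.

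**Step 3. Simulation.** 200,000 eyes per scenario. Assumed: pre-operative 1.5 to 3.5 D (uniform); control incision effect 0.1 to 0.5 D at a random axis; Toric predicted residual 10% of pre-operative; post-operative error SD 0.2 or 0.3 D per component.

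| Mean (range over scenarios) | Non-Toric | Toric |
|---|---|---|
| Correction index | 1.09 to 3.86 | 1.00 to 1.01 |
| SD of index | 0.38 to 2.02 | 0.10 to 0.14 |
| TIA − SIA (D) | −0.29 to −0.04 | −0.02 to −0.01 |
| SIA (D) | 0.27 to 0.60 | 2.26 to 2.27 |
| Residual astigmatism (D) | about 2.5 | 0.34 to 0.44 |

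Between 58% and 95% of non-Toric eyes have an index above 1.

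**Step 4. Direction of a between-arm test.** With 55 per arm, pre-operative 1.75 to 3.75 D and error SD 0.25 D, an independent t-test on the index was significant in 100% of 2,000 runs with an incision effect of 0.25 D, and in 54% with 0.50 D. In every significant run the non-Toric index was the higher. The same test on residual magnitude had power of about 1.00.

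**Step 5. Refractive instead of corneal input.** If pre-operative refractive cylinder is entered, it includes the natural lens. With an assumed lenticular SD of 0.3 to 0.8 D per component, control TIA averages 0.38 to 1.00 D and the median index falls from 1.30 to 1.05. It is steadier, but still near 1, and what it describes is removal of the natural lens, not correction by the implant.

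**Step 6. Common zero-residual target.** TIA is then 2.75 D in both arms. The first non-Toric eye scores 0.25/2.75 = 0.09 and the Toric eye 2.35/2.75 = 0.855, which is the right order.

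**The case against.** Four objections carry weight.

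- **A reader might infer that the astigmatism analysis as a whole cannot show the Toric benefit.** The documents do not support that. Equation 4 uses no target, and SIA separates the arms by about 1.7 to 2.0 D in Step 3 (2.27 − 0.60 = 1.67; 2.26 − 0.27 = 1.99). The same table row lists cylinder under a mixed ANOVA between groups and compares unaided acuity. Post-operative cylinder magnitude is residual astigmatism. What remains is that cylinder appears only in a list of collected data, while the analysis named for post-operative astigmatism is the Alpins set.
- **A reader might infer that a Toric against non-Toric test of the index is definitely planned.** The wording is a dependent t-test in the two groups. That could mean a paired analysis within each arm, which suits an accuracy metric. If it does mean a comparison of arms, a paired test does not fit, because the arms contain different patients. Under either reading a control-arm index is computed and reported.
- **A reader might take 2.5 D left as a fact about the trial.** It is an example. The documents support only about 1.5 D or more, and that depends on applying the Section 6.2 criterion to each eye.
- **Near-zero control TIA depends on the input.** The plan does not say whether the pre-operative value is corneal or refractive, and Step 5 shows that the instability shrinks with refractive values. The problem of meaning does not.

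**Conclusion.** The point holds for three quantities: the correction index, the scalar TIA − SIA difference, and the SIA–TIA correlation in the non-Toric arm. They measure accuracy against each eye's own prediction. Under the assumptions above, the control arm scores an average index of 1.09 to 3.86 with its astigmatism essentially uncorrected, against about 1.00 in the Toric arm. The existence of the problem follows from the equations and from Section 1. Its size depends on the incision effect, the prediction error and the type of pre-operative input, none of which the plan states. The reading that each arm has its own target is the natural one, but the plan should say so.

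This is a secondary outcome. The primary endpoint and the sample size do not depend on it. It is worth correcting because the result could mislead and the correction is nearly free.

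**What to change.** In Section 10.3.3:

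1. Name post-operative residual refractive astigmatism at study visit 3 (magnitude, with J0 and J45) as the between-arm astigmatism outcome. Compare it with an independent-groups test, using one value per participant or a model that allows for two eyes.
2. Report the correction index, the difference from target and the SIA–TIA correlation in the Toric arm only, labelled as lens accuracy. Alternatively, set a common zero-residual target for both arms in Equation 3.
3. State whether pre-operative values are corneal or refractive, and how the predicted residual is obtained.
4. Compute the difference from target as the length of the vector difference. Equation 6 ignores axis: an assumed Toric eye with the full 2.75 D effect placed 15° off axis scores index 1 and difference 0 with 2 × 2.75 × sin 15° = 1.42 D left.

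The cost is SAP wording. Sphere, cylinder and axis are already recorded in both arms, so no visit or test is added. What is lost is a between-arm correction index that has no useful meaning.

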### Risks

For Toric IOLs to correct astigmatism, they need to be placed specifically with reference to the steepest meridian of the eye. All IOLs can rotate, but rotation of Toric IOLs can affect its astigmatism correction effect. Small rotations do not affect the astigmatic power, but larger rotations will reduce the astigmatism correcting effect. If the IOL is rotated 30 degrees, the astigmatism correcting effect is eliminated (Visser et al., 2013). In approximately 1% of patients, the Toric lens rotates significantly reducing the level of astigmatism that is corrected by the Toric lens. If this is the case, and the participant is unhappy with their visual outcome, the surgeon will discuss the possibility of a secondary procedure to reposition the lens. The surgeon will discuss the risks of the repositioning procedure with the participant to determine if the benefits outweigh the risks. It is important to note that this repositioning (to correct any unwanted astigmatism) is only possible with Toric lenses, with standard IOLs unwanted astigmatism will not be corrected. Even with significant Toric IOLs rotation, additional surgery is generally not required as by removing the cataract, the rotated Toric IOLs still provide significant improvement in vision and the remaining astigmatism can be corrected with spectacles.

The mobility assessment involves walking over obstacles, turning, going up and down stairs. The participants will have three small portable motion sensors placed on their neck and lower back and will be asked to wear a pair of eye tracking glasses during the mobility tasks. There is a very low risk of falls, similar as during any normal activities of daily living. The risk will be minimal as all assessment will be carried out under the supervision of an experienced physiotherapist. Also, the assessment venues are part of the University campus which is regularly controlled to maintain environmental safety and has provision of first aid equipment. A patient and public involvement discussion has been conducted which covered discussion about assessments and the research design. All participants were supportive about the research idea and felt the research could raise awareness of available choice of IOLs. Participants were asked about the practicality of the research and felt it would be better to have all assessments done in one site. The assessments were to be conducted at Marjon Biomechanics Lab and

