#### Post-operative complications:

- endophthalmitis (inflammation of the internal eye tissues, most commonly caused by an infection) and bleeding.
- irregular astigmatism
- dry eye
- keratectasia (progressive myopia, irregular astigmatism, ghosting, fluctuating vision and problems with scotopic vision. The progression leads to severe loss of corrected visual acuity)
- Patient reported subjective complaints of halos, glare, and ghost images.
- Wound leak
- Flat anterior chamber
- Hyphema
- Vitreous in anterior chamber
- Vitreous in wound

Vision and balance changes after bilateral implantation of Toric IOLs  
IRAS ID: 286913

- Raised IOP
- Pupillary block
- Anterior synechiae
- Posterior synechiae
- Deposits on IOL
- Fibrin in Pupil
- Nuclear remnants
- Cortical Remnants
- Retinal detachment
- Cystoid macular oedema
- Anterior capsular Opacification
- Posterior capsular opacification
- Intraocular lens tilt and decentration
- Cells/flare in the anterior chamber

Toric IOLs have a few other potential complications. Astigmatism may be overcorrected or under-corrected.

As mentioned previously, the Toric IOL may rotate off-axis. There will be some partial effect if it rotates off-axis. For example, the correction effect of the Toric IOLs is reduced by 10% for every 3° rotation off-axis. For the lens to lose its full effect, it would have to be off axis by 30°. Prevention of IOL rotation includes complete removal of Ophthalmic Viscosurgical Devices (OVDs), especially posterior to the IOL.

Most patients do extremely well following this surgical technique. The technical surgical learning curve for the surgeon is minimal for an outcome that is reliably predictable. Toric IOLs, exclusively or in conjunction with astigmatic keratotomy and/or strategic cataract incision placement, can result in excellent management of astigmatism.

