#### 10.4 Subgroup analyses

Within the Toric IOLs group, a subgroup of participants presented with post-surgery IOL rotation > 5 degree will be isolated to compare the outcomes. This subgroup of participants is very likely to need

Vision and balance changes after bilateral implantation of Toric IOLs  
IRAS ID: 286913

another adjustment surgery. Their data will inform the impact of IOLs rotation on surgery complications and whether such rotation may be related to degree of astigmatism.

In both the Toric IOLs and non-Toric IOLs group, subgroups of different degree of astigmatism: mild (<1.50), moderate (1.5-3.0) and severe (3.0+) will be differentiated to compare the outcomes to help inform if Toric IOLs offer similar beneficial effect across cataract patients with wide range of astigmatism. This will help to identify which patients should be referred for Toric IOLs and support evidence-based practice.

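### Equation 6 subtracts two lengths, so the planned difference vector is a signed magnitude error that cannot register axis error

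*Combined protocol and SAP*

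**What the plan says.** In section 10.3.3, the refraction row of the table and its footnote commit the trial to a vector analysis: "Post-operative refractive astigmatism will be analysed using the Alpins method", and "Cylindrical power and axis will be converted to vectors (J0 and J45; Equations 1 & 2"). Equation 3 then gives TIA as the square root of the summed squared differences between pre-operative and predicted residual J0 and J45. Equation 4 gives SIA in the same way, with post-operative values in place of the predicted ones. Equation 5, the correction index, is SIA/TIA. The text then says that the "difference vector is the difference between TIA and SIA (Equation 6"), and Equation 6 itself reads "Difference Vector = TIA - SIA". No equation gives an angle of error or a component-wise difference.

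Elsewhere the plan says how strongly axis error matters. Section 2.1 (Risks): "If the IOL is rotated 30 degrees, the astigmatism correcting effect is eliminated". Section 9.5: "the correction effect of the Toric IOLs is reduced by 10% for every 3° rotation off-axis". Section 10.4 sets up a rotation subgroup: "a subgroup of participants presented with post-surgery IOL rotation > 5 degree will be isolated to compare the outcomes".

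**The concern.** A square root of summed squares keeps size and discards direction. Once TIA and SIA are lengths, subtracting them cannot give a vector, or the length of one. It gives only the shortfall or excess in the size of the correction. For given lengths, Equations 5 and 6 take the same values whatever the axis error.

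Rotation of a correctly powered Toric lens is the case in which the achieved correction keeps its size and changes direction. An analyst who codes the formula as printed would report no error for a misaligned lens. The same would happen in the rotation subgroup of section 10.4, if this metric is among the outcomes compared there. Because the quantity is signed, over- and under-corrections can also cancel in a group mean.

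A smaller wording gap sits in the same table cell: "dependent t-tests will be used to analyse the remaining metrics in the two groups" does not say which values are paired, or how these metrics are compared between arms.

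**Working it through.** **Inputs from the plan.** Equations 1 and 2: J0 = J cos 2a and J45 = J sin 2a. Equations 3 to 6 as above. Rotation figures: 10% lost per 3 degrees (section 9.5) and all lost at 30 degrees (sections 2.1 and 9.5).

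**Assumptions, not plan figures.** TIA of 1.5, 2.0 and 3.0 D (1.5 and 3.0 are the limits of the moderate band in section 10.4); the rotation angles (5 degrees is the section 10.4 threshold); and, where used, an under-correction of 0.25 D.

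**Step 1: the vector difference.** The TIA vector is Pre − Predicted and the SIA vector is Pre − Post, so their difference is Post − Predicted. With lengths T and S and axis error θ (doubled by Equations 1 and 2):

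|DV| = sqrt(T² + S² − 2·T·S·cos 2θ)

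When S = T this becomes 2·T·sin θ. Equation 6 is T − S and Equation 5 is S/T; neither contains θ.

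**Step 2: reproduce the plan's own figures.** With S = T, the vector difference as a share of TIA is 2 sin 3° = 10.5% at 3 degrees (plan: 10%) and 2 sin 30° = 100% at 30 degrees (plan: eliminated). The component-wise metric agrees with the plan's account of rotation; Equation 6 gives 0% at both.

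**Step 3: one case through Equations 1 to 6.** Pre-operative 2.0 D at axis 90°: (J0, J45) = (−2, 0). Predicted residual: (0, 0). A 2.0 D correction delivered 30° off, at axis 120°: (−1, −1.732).

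- Post = (−2, 0) − (−1, −1.732) = (−1, 1.732), a cylinder of 2.0 D.
- TIA = sqrt(2² + 0²) = 2.0 D.
- SIA = sqrt((−2 + 1)² + (0 − 1.732)²) = sqrt(1 + 3) = 2.0 D.
- Equation 5 = 1 and Equation 6 = 0 D.
- |Post − Predicted| = sqrt(1 + 3) = 2.0 D.

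The eye has as much cylinder as before surgery, and both planned indices report a perfect result.

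**Step 4: size across the assumed range.**

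| Case | Rotation | Equation 6 | True, T = 1.5 D | T = 2.0 D | T = 3.0 D |
|---|---|---|---|---|---|
| S = T | 5° | 0 | 0.26 | 0.35 | 0.52 |
| S = T | 10° | 0 | 0.52 | 0.69 | 1.04 |
| S = T | 30° | 0 | 1.50 | 2.00 | 3.00 |
| S = T − 0.25 | 0° | 0.25 | 0.25 | 0.25 | 0.25 |
| S = T − 0.25 | 5° | 0.25 | 0.35 | 0.41 | 0.56 |
| S = T − 0.25 | 10° | 0.25 | 0.54 | 0.70 | 1.03 |

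(All in dioptres.) A non-zero predicted residual does not help. With 0.5 D predicted and a 2.0 D correction, Equation 6 is still 0 at 5, 10 and 30 degrees, against 0.35, 0.69 and 2.00 D.

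**Step 5: sign.** For T = 2.0 D on axis, a 20% under-correction gives Equation 6 = +0.40 D and a 20% over-correction gives −0.40 D. The true length is 0.40 D in both cases, yet the two signed values average to zero. With 20% over-correction and 10 degrees off axis, Equation 6 gives −0.40 D against a true 0.86 D.

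**The case against.** The strongest reply is that this is shorthand. The footnote speaks of vectors, and the authors may have meant vector subtraction and printed magnitudes. That may be so, but the plan gives TIA and SIA no other definition, and code written from the equations produces the scalar.

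The second reply is that axis error is captured elsewhere. Rotation is a listed secondary endpoint (section 3.5) with its own summary and Bland-Altman analysis, cylinder and axis are recorded, and the rotation subgroup is defined by measured rotation. This stands as a limit on the consequence. But rotation is recorded for the Toric arm only and describes lens position; it is not residual astigmatic error in dioptres.

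Third, the effect is mainly in one arm and the large values are rare. If a non-Toric lens is predicted to leave astigmatism unchanged (an assumption), TIA is 0, Equation 6 gives −SIA and the true length is SIA, so only the sign is wrong. Section 2.1 puts significant rotation at about 1%, which is 0.01 × 70 = 0.7 of the 70 Toric participants. Both points stand; the 30 degree example shows the mechanism, not a typical eye.

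Fourth, sections 2.1 and 9.5 describe lens behaviour and do not mention Equation 6, so they do not contradict it word for word. That is correct. The contradiction in the text is between a declared vector method and a scalar formula; the rotation figures show what the scalar misses.

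On the t-tests, the phrase can be read as paired tests within each arm, and the same cell names mixed ANOVA for refraction outcomes. That point is subordinate and concerns missing detail.

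**Conclusion.** The concern holds. As printed, Equation 6 does not compute a difference vector and is blind to axis error, as is the correction index. This follows from the algebra and needs no assumption. The dioptre sizes do rest on the assumed TIA, rotation and under-correction. At the plan's own 5 degree threshold the omitted error is about 17% of TIA (2 sin 5° = 17.4%) when the achieved size equals the target.

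The reach is limited to a derived metric that appears only in the analysis table and its footnote, not in the endpoint lists. No data are lost. It should be corrected before analysis, so that a misaligned lens is not reported as fully corrected under the name of a vector measure.

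**What to change.** Replace Equation 6 with

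DV = sqrt((PostOp J0 − Predicted residual J0)² + (PostOp J45 − Predicted residual J45)²)

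If TIA − SIA is kept, give it a name that says what it is, such as signed difference in magnitude.

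In the same edit, state which values the dependent t-tests pair (for example, SIA against TIA within an arm). Name an independent-groups test or model for any Toric versus non-Toric comparison of these metrics, and say how two eyes from one participant are handled.

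The cost is a few lines of SAP wording and one line of code. All the J0 and J45 components are already used in Equations 3 and 4, so no new measurement is needed.
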